Photographs will remain unretouched. One blinded dermatologist and one unblinded dermatologist will rate the patient's severity of jowling based on the Jawline Rating Scale (JRS) (1) at baseline, the 4-week, 8-week, and 12 or 16-week visits. The patient will also rate their jowling based on the JRS as well as their satisfaction with the procedure.

Analysis of Scientific Soundness of the Protocol

The proposed study has been designed to provide a valid method to analyze the safety and efficacy of facial volume replacement. Measure taken to assure that the study provides valid data are as follows:

- 1. Photographs will be taken under standardized conditions. Photographs will be taken with a VISIA CR, a device made by Canfield Scientific specifically to be utilized for clinical research to provide uniformity in patient photographs.
- 2. Adverse or unanticipated effects that occur during the course of this clinical study will be recorded and carefully analyzed as to their relationship to the treatment.
- 3. Evaluators will review individual photos without knowledge of if they are before or after photos.

Primary Outcome Measure:

The primary outcome is a reduction of 1 or more points of the Jawline Rating Scale (JRS)
 Assessment (on scale of 0 to 4) at baseline versus that at 4 weeks from the last injection (whether initial or touch-up) based on any or all of one blinded dermatologist rating, one unblinded dermatologist rating, and patient rating. (A lower number will mean a better outcome) Time Frame: Baseline to 4 weeks after last injection.

Secondary Outcome Measures

- 1. Reduction of 1 or more points of the Jawline Rating Scale (JRS) Assessment (on scale of 0 to 4) at baseline versus that at 4 weeks from the last injection based on the patients rating while looking in the mirror and at before and after photographs. A lower number will mean a better outcome. Time Frame: 4 weeks from last injection
- 2. Whether group 1 and group 2 has a higher reduction in the Jawline Rating Scale (JRS) (on scale of 0 to 4) at 4 weeks from the lastinjection compared to baseline based on ratings from one blinded dermatologist and one unblinded dermatologist. A lower number will mean a better outcome. Time Frame: 4 weeks from last injection

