- 3. Whether group 1 or group 2 has a higher reduction in the Jawline Rating Scale (JRS) (on scale of 0 to 4) at 4 weeks from the last injection compared to baseline based on the patients rating while looking in the mirror and at before and after photographs. A lower number will mean a better outcome. Time Frame: 4 weeks from last injection
- 4. Jawline Rating Scale (JRS) Assessment on scale of 0 to 4 at 4 weeks: One blinded dermatologist and one unblinded dermatologist will rate the patient's severity of jowling based on the Jawline Rating Scale (JRS). The patient will also rate their jowling based on the Jawline Rating Scale (JRS). The scale is on a rating of 0 to 4. A lower number will mean a better outcome. [Time Frame: 4 weeks]
- 5. Jawline Rating Scale (JRS) Assessment on scale of 0 to 4 at 8 weeks: One blinded dermatologist and one unblinded dermatologist will rate the patient's severity of jowling based on the Jawline Rating Scale (JRS). The patient will also rate their jowling based on the Jawline Rating Scale (JRS). The scale is on a rating of 0 to 4. A lower number will mean a better outcome. [Time Frame: 8 weeks]
- 6. Jawline Rating Scale (JRS) Assessment on scale of 0 to 4 at 12 or 16 weeks: One blinded dermatologist and one unblinded dermatologist will rate the patient's severity of jowling based on the Jawline Rating Scale (JRS). The patient will also rate their jowling based on the Jawline Rating Scale (JRS). The scale is on a rating of 0 to 4. A lower number will mean a better outcome. [Time Frame: 3 months from last treatment]
- Incidence of abnormal eye exam (Confrontational Visual Fields Exam) findings (Safety):
 Ophthalmologic exams that include Confrontational Visual Fields Exam will be performed prior to any
 treatment, 30 minutes after treatment, and at all follow up in-person visits. [Time Frame: up to 18
 months]
- 8. Incidence of abnormal eye exam (Snellen Eye Exam) findings (Safety):
 Ophthalmologic exams that include Snellen Eye Exam will be performed prior to any treatment, 30 minutes after treatment, and at all follow up in-person visits. [Time Frame: up to 18 months]
- 9. Incidence of abnormal eye exam (Ocular Motility Exam) findings (Safety):
 Ophthalmologic exams that include Ocular Motility Exam will be performed prior to any treatment,
 30 minutes after treatment, and at all follow up in-person visits. [Time Frame: up to 18 months]

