		ment	Follow	Office	Office	Follow	office	Office	medicine	medicine
			Up Call	Follow	Follow	Up Call	Follow	Follow	Video	Video Call
				Up	Up		Up	Up	Call	
			72 hours	2	4	72	8	16	6	12
			after	weeks	weeks	hours	weeks	weeks	months	months
			treat	+/- 3	+/- 3	after	+/- 3	+/- 3	after RTx	after RTx
			ment	days	days	RTx	days	days	+/- 3 days	+/- 3 days
Informed Consent	Х									
Inclusion/Exclusion										
	Х									
Medical History	X								0	
Urino Drognanov	^									
Urine Pregnancy Test	X	Х			Х					
	^	^			^					
Photography		Х		Х	Х		Х	Х		
Blinded Evaluation	Х				х		х	х		
Adverse Events		Х	Х	Х	Х	х	Х	х	X	Х
Physical Exam			Λ	Λ	, , , , , , , , , , , , , , , , , , , 		, , , , , , , , , , , , , , , , , , , 			, A
r nysicai Exam		Х		Х	Х		X	X		
Safety Eye		, A		Λ	Λ		, A	^		
Assessments		X**		Х	Х		X	X		
Cranial Nerve		 ^						 ^		
Assessments		Х		X	X		X	Х		
Patient				,	,			 		
Questionnaire/	Х			X	Х		Х	Х	X	X
Evaluation	`				``		^	^`		
Patient Pain										
Evaluation		X	X	Х	X	Х	Х	Х	Х	X
Patient Safety				- •	- •	1				
Diary***		X	X		X	Х				
Retreatment		 	,			 				
Retreatment					X*					

^{*}If requested by physician or patient and agreeable to both

^{**}Safety Eye Assessments will be performed prior to treatment and 30 minutes after treatment

^{***}Patient diary to be completed daily by email for 30 days following treatment

Voluma Jowl/Jawline Study 10001 Appendix 1: Study Schematics No Retreatment

Visit #	1	2	3	4	5	6	7	8	9
	Screening	Treat	Safety	In	In	In	In	Tele	Tele
		ment	Follow	Office	Office	office	Office	medicine	medicine
			Up Call	Follow	Follow	Follow	Follow	Video	Video
				Up	Up	Up	Up	Call	Call
			72	2	4	8	12	6	12
			hours	weeks	weeks	weeks	weeks	months	months
			+/- 4	+/- 3	+/- 3	+/- 3	+/- 3	after Tx	after Tx
			hours	days	days	days	days	+/- 3	+/- 3
								days	days
Informed Consent	X								
Inclusion/Exclusion									
	X								
Medical History									
	X								
Urine Pregnancy									
Test	X	Х							
Photography									
		Х		Χ	Х	X	Χ		
Blinded Evaluation									
	X				Х	Х	Х		
Adverse Events									
		Х	Х	Х	Х	Х	Х	Х	Х
Physical Exam									
,		Х		Χ	Х	Х	Χ		
Safety Eye									
Assessments		Χ*		Χ	Х	Х	Χ		
Cranial Nerve									
Assessments		Х		Х	Х	Х	Х		
Patient									
Questionnaire/	Х			Х	Х	Х	Х	Х	Х
Evaluation									
Patient Pain									
Evaluation		Х	Х	Х	Х	Х	Х	Х	Х
Patient Safety									
Diary**		Х	Х						
Retreatment***									

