^{*} Safety Eye Assessments will be performed prior to treatment and 30 minutes after treatment

^{**}Patient diary to be completed daily by email for 30 days following treatment

^{***}No Retreatment done per patient and/or physician

advanced Jowl Improvement with Injectable Fillers: Jawline Injections alone vs Jawline and Cheek Injections

Blinded Physician Assessment

Patient Number	Date:			
Baseline or Date pos Baseline or Date Pos	t 1 st Injection: Baselin st 2 nd Injection: Baselin	e4w8w_ ne4w8w_	12 week 16 12 week 16	16 week sweek
No.	OMAZ -	- CMAZ	CMAZ	SMB2
OMerz O	- OMerz	CMerz CMerz	GMerz S	©Merz.
0	1	2	3	4
No sagging	Mild sagging	Moderate sagging	Severe sagging	Very severe sagging
pictured above, put a	etructions: Without reference X by the value you 3 4	feel represents the a		
the patient prior to in	jection and the photogoutting an X by the varied	graph of the patient to	oday, please evaluate	
Comments:				
Blinded Physician: Date:	Name	Sig	nature	

advanced Jowl Improvement with Injectable Fillers: Jawline Injections alone vs Jawline and Cheek Injections 10001

Subject Self-Assessment of Results

Patient Number				
Date:				
Baseline or Date post Or: Date Post 2 nd Injection	-	line 4 w 8 8w 12 w_		16 week
©Merz ©Merz	OMerz	SMerz	CMerz CMerz	CMerz CMerz
3	1	1	3	1
0	1	2	3	4
No sagging	Mild sagging	Moderate sagging	Severe sagging	Very severe sagging
Grading of Jowls Instructured above, put an				
1 2	34	_ 5		
Grading of Jowls by p yourself prior to inject putting an X by the va	ion and the photogra	ph of yourself today, p	olease evaluate your	
Much improved Improved No change Worse Much Worse	-			
Comments:				
Signature of Coordi	nator	Date:		

	Iowl/Jawline Study Iumber	10001-Patient Diary		Date
	e treatment			
many da	ys it has been since	= :	ne questions v	patient number, the date, and how which require to answer mild,
• N	Moderate: minimal,	and/or local or noninva out not immediately life	sive intervent	only; no intervention needed tion needed nospitalization or prolongation of
Have y	you experien	ced any of the fo	ollowing s	symptoms?
	oderate to Severe Di yes was it Mild	zziness Moderate		NO
	onfusion yes was it Mild	Moderate		NO
		s in your arms or legs Moderate		
	nanges to consciousn yes was it Mild	ess or alertness Moderate		NO
		eech impairment Moderate		
If		Moderate	Severe	
				bove questions, pleas
 1811 91 2 2 2 2 2 2 2 2 2 2 2 2 2 2 2 2 2 	L1 and seek i	mmediate medi	cal attent	ion.

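### Two inconsistencies in the use of the jawline scale: entry is grades 1–3 in one section and 2–3 in another, and the patient form's answer line appears to run 1–5 on a 0–4 scale (to be checked on the original form)

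*Combined protocol and SAP*

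**What the plan says.** **Entry range.** The Protocol Summary describes 16 women with sagging of grades 1 to 3. Patient Selection item 1 asks for grade 2 to 3, as judged by both the physician evaluator and the patient. Both cite reference 1, which is also the reference given for the Jawline Rating Scale (JRS). The Pre-Procedure Evaluation section makes enrolment depend on passing all inclusion and exclusion criteria.

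**Scale range.** The primary outcome and secondary outcomes 1 to 6 place the JRS on 0 to 4. For the patient rating, items 4 to 6 state: "The patient will also rate their jowling based on the Jawline Rating Scale (JRS). The scale is on a rating of 0 to 4". Response is a fall of one point or more from baseline to 4 weeks after the last injection. The primary outcome is "based on any or all of one blinded dermatologist rating, one unblinded dermatologist rating, and patient rating". Secondary outcome 1 is "based on the patients rating while looking in the mirror and at before and after photographs", and outcome 3 compares the groups on that same rating.

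**Patient form.** The Subject Self-Assessment form carries five pictures labelled 0 to 4 with the words "No sagging Mild sagging Moderate sagging Severe sagging Very severe sagging". In the available text, the answer line below them reads 1, 2, 3, 4, 5. The header, "Baseline or Date post Or: Date Post 2 nd Injection", shows that the same form serves baseline and follow-up. A second item asks for improvement against the pre-injection photograph, with the choices "Much improved Improved No change Worse Much Worse".

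**Timing.** Both Appendix 1 schedules, including "Voluma Jowl/Jawline Study 10001 Appendix 1: Study Schematics No Retreatment", mark the patient evaluation row at screening and not at the treatment visit. The screening rating therefore appears to serve as both the patient's entry grade and her baseline.

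**The concern.** The entry conflict means that a woman at grade 1 is eligible under one section and ineligible under the other. It also bears on the endpoint: from grade 1, the only way to respond is to reach 0.

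The form matters because the patient rating is the whole of the data for secondary outcomes 1 and 3, part of outcomes 4 to 6, and one of the three ratings in the primary outcome. If the primary is read as any one rating, a single false patient response could create a primary response. If it is read as all three, a single lost one could remove it. Five boxes numbered 1 to 5 under five pictures numbered 0 to 4 would invite two ways of marking: by the number under the picture (label) or by the box in the same position (position). These differ by one grade, which is the response threshold.

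**Working it through.** The plan gives no figure to reproduce here. The sample size of 16 carries no stated power, effect size or standard deviation, and this point needs none of them.

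**Inputs.** 16 patients (Study Design, Scope); 1:1 allocation (Protocol Summary); scale 0 to 4 and a one-point threshold (Primary Outcome Measure); patient entry grade 2 to 3 (Patient Selection item 1).

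**Step 1: is the 1–5 line certain?** No. The form pages came through badly. The Blinded Physician Assessment line survives only inside a broken sentence, "Without reference X by the value you 3 4", so digits were lost there. The patient form also carries a row of digits 3, 1, 1, 3, 1 between the picture captions and the true labels, which nothing in the protocol explains, so stray digits appear as well. The physician line cannot serve as a contrast either: it ends at 4 in this text, but trailing digits may have gone the same way as the leading ones. There are two cases:
- *A 0 is printed (line 0–5).* Position and label agree. The only defect is a surplus box, 5, with no picture or meaning. Every figure below is then 0.
- *The line is truly 1–5.* Steps 2 and 3 apply.

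**Step 2: consequences of a true 1–5 line.** Label mark = grade, taking the lowest box, 1, as the mark when the grade is 0. Position mark = grade + 1. The patient half of the 2–3 entry rule requires a screening mark of 2 or 3.

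| Marking (baseline, week 4) | Her grade | Marks | Recorded fall | True fall | Effect |
|---|---|---|---|---|---|
| Label, label | 2 to 0 | 2, 1 | 1 | 2 | response kept, understated by 1 |
| Label, label | 3 to 0 | 3, 1 | 2 | 3 | response kept, understated by 1 |
| Label, label | 1 to 0 (1–3 entry only) | 1, 1 | 0 | 1 | response lost |
| Position, position | 2 to 1 | 3, 2 | 1 | 1 | change correct, both scores 1 too high |
| Position, label | 2 to 2 | 3, 2 | 1 | 0 | false response |
| Position, label | 1 to 1 | 2, 1 | 1 | 0 | false response, if the physician grade is 2–3 |
| Position, label | 3 to 3 | 4, not enrolled | – | – | fails the patient half of entry |
| Label, position | 2 to 1 | 2, 2 | 0 | 1 | response lost |
| Label, position | 3 to 2 | 3, 3 | 0 | 1 | response lost |

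Under 2–3 entry, then, the missing 0 on its own loses no one-point responder. Consistent position marking leaves change scores intact but raises the patient's absolute scores in outcomes 4 to 6, and her entry rating, by one grade: a self-perceived 1 would pass as 2, and a self-perceived 3 would fail as 4. Only switching produces false responses, and it can also hide an improvement of exactly one point.

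**Step 3: size per patient.**
- Patients per arm: 16/2 = 8.
- One misclassified patient: 1/8 = 12.5 percentage points in her arm's patient response rate; 1/16 = 6.25 points over all 16.
- One label-marker who reaches 0: her reduction is understated by 1, which is 1/8 = 0.125 in her arm's mean change.
- One consistent position-marker: 1/8 = 0.125 in her arm's mean patient score in each of outcomes 4 to 6, and 0 in mean change.

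The documents give no rate of switching or position marking, and none is assumed.

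**Step 4: entry range.** Grades 1–3 set beside grades 2–3, on the same cited scale, differ by exactly one grade, and neither text is damaged. The documents do not say how many grade-1 women might be affected.

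**The case against.** The strongest case against the form point is that it rests on unreliable text. Digits are both dropped and added on these pages, so neither the missing 0 nor the extra 5 can be settled from what is available. That stands, and it is why the form point is conditional. The pictures, their labels, the words beneath them and the separate improvement item also make a change of convention between visits less likely, and the 12.5 points is simply what any one patient contributes in an arm of 8.

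On entry, the Pre-Procedure Evaluation section makes the inclusion and exclusion criteria operative, so the mismatch may amount to loose wording in a summary. That limits the practical effect but does not remove the conflict.

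A reader might infer more than the documents support:
- *That the patient-rated outcomes are invalid, or that the form certainly lacks a 0.* The damaged text does not show this.
- *That the physician form is correctly numbered and so proves the patient form wrong.* Its line is too broken to show this.
- *That the missing 0 loses responders.* Under 2–3 entry it does not; that needs a grade-1 entrant, whom the criteria exclude.
- *That the comparison of the two groups is biased.* Both groups use the same form, and nothing suggests that marking habits differ by group. For outcome 3, any switching would be noise, not an expected bias.

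**Conclusion.** Both inconsistencies stand and should be fixed, with different degrees of certainty.

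The entry-range conflict is certain. Its practical effect is limited by the enrolment rule and cannot be quantified from the documents.

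The form point is probable but unconfirmed. If a 5 is printed, the form is wrong whether or not a 0 is also printed. The harm to the data, however, depends on the line being truly 1–5 and on how patients mark it. On that assumption, each misclassified patient shifts her arm's patient response rate by 12.5 points, and each consistent position-marker carries a one-grade shift in outcomes 4 to 6. The number affected may be none. The reading of the screening rating as the baseline rests on the Appendix 1 schedules; the protocol text does not say so outright.

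**What to change.** 1. Check the original Subject Self-Assessment form. Make the answer boxes read 0, 1, 2, 3, 4, each under its matching picture.
2. If ratings were already made on a true 1–5 form, compare each follow-up mark with the improvement item on the same form, in both directions: a one-grade fall beside no change, and no fall beside either of the improved choices. Whoever runs the query should not know the study arm. Keep the original marks on file, because a later answer rests on recall and a genuine improvement can be smaller than one grade. This query cannot detect a patient who marked one grade high throughout, so the patient scores in outcomes 4 to 6 would need that caveat.
3. Reconcile the Protocol Summary and Patient Selection item 1 to a single entry range. The choice is the sponsor's.

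The cost is one look at the form, a reprint if needed, and one wording change. If 1–5 forms were used, at most 16 patients' forms need the query.

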		ment	Follow	Office	Office	Follow	office	Office	medicine	medicine
			Up Call	Follow	Follow	Up Call	Follow	Follow	Video	Video Call
				Up	Up		Up	Up	Call	
			72 hours	2	4	72	8	16	6	12
			after	weeks	weeks	hours	weeks	weeks	months	months
			treat	+/- 3	+/- 3	after	+/- 3	+/- 3	after RTx	after RTx
			ment	days	days	RTx	days	days	+/- 3 days	+/- 3 days
Informed Consent	Х									
Inclusion/Exclusion										
	Х									
Medical History	X								0	
Urino Drognanov	^									
Urine Pregnancy Test	X	Х			Х					
	^	^			^					
Photography		Х		Х	Х		Х	Х		
Blinded Evaluation	Х				х		х	х		
Adverse Events		Х	Х	Х	Х	х	Х	х	X	Х
Physical Exam			Λ	Λ	, , , , , , , , , , , , , , , , , , , 		, , , , , , , , , , , , , , , , , , , 			, A
r nysicai Exam		Х		Х	Х		X	X		
Safety Eye		, A		Λ	Λ		, A	^		
Assessments		X**		Х	Х		X	X		
Cranial Nerve		 ^						 ^		
Assessments		Х		X	X		X	Х		
Patient				,	,			 		
Questionnaire/	Х			X	Х		Х	Х	X	X
Evaluation	`				``		^	^`		
Patient Pain										
Evaluation		X	X	Х	X	Х	Х	Х	Х	X
Patient Safety				- •	- •	1				
Diary***		X	X		X	Х				
Retreatment		 	,			 				
Retreatment					X*					

^{*}If requested by physician or patient and agreeable to both

^{**}Safety Eye Assessments will be performed prior to treatment and 30 minutes after treatment

^{***}Patient diary to be completed daily by email for 30 days following treatment

Voluma Jowl/Jawline Study 10001 Appendix 1: Study Schematics No Retreatment

Visit #	1	2	3	4	5	6	7	8	9
	Screening	Treat	Safety	In	In	In	In	Tele	Tele
		ment	Follow	Office	Office	office	Office	medicine	medicine
			Up Call	Follow	Follow	Follow	Follow	Video	Video
				Up	Up	Up	Up	Call	Call
			72	2	4	8	12	6	12
			hours	weeks	weeks	weeks	weeks	months	months
			+/- 4	+/- 3	+/- 3	+/- 3	+/- 3	after Tx	after Tx
			hours	days	days	days	days	+/- 3	+/- 3
								days	days
Informed Consent	X								
Inclusion/Exclusion									
	X								
Medical History									
	X								
Urine Pregnancy									
Test	X	Х							
Photography									
		Х		Χ	Х	X	Χ		
Blinded Evaluation									
	X				Х	Х	Х		
Adverse Events									
		Х	Х	Х	Х	Х	Х	Х	Х
Physical Exam									
,		Х		Χ	Х	Х	Χ		
Safety Eye									
Assessments		Χ*		Χ	Х	Х	Χ		
Cranial Nerve									
Assessments		Х		Х	Х	Х	Х		
Patient									
Questionnaire/	Х			Х	Х	Х	Х	Х	Х
Evaluation									
Patient Pain									
Evaluation		Х	Х	Х	Х	Х	Х	Х	Х
Patient Safety									
Diary**		Х	Х						
Retreatment***									

^{*} Safety Eye Assessments will be performed prior to treatment and 30 minutes after treatment

^{**}Patient diary to be completed daily by email for 30 days following treatment

^{***}No Retreatment done per patient and/or physician

advanced Jowl Improvement with Injectable Fillers: Jawline Injections alone vs Jawline and Cheek Injections

Blinded Physician Assessment

Patient Number	Date:			
Baseline or Date pos Baseline or Date Pos	t 1 st Injection: Baselin st 2 nd Injection: Baselin	e4w8w_ ne4w8w_	12 week 16 12 week 16	16 week sweek
No.	OMAZ -	- CMAZ	CMAZ	SMB2
OMerz O	- OMerz	CMerz CMerz	GMerz S	©Merz.
0	1	2	3	4
No sagging	Mild sagging	Moderate sagging	Severe sagging	Very severe sagging
pictured above, put a	etructions: Without reference X by the value you 3 4	feel represents the a		
the patient prior to in	jection and the photogoutting an X by the varied	graph of the patient to	oday, please evaluate	
Comments:				
Blinded Physician: Date:	Name	Sig	nature	

advanced Jowl Improvement with Injectable Fillers: Jawline Injections alone vs Jawline and Cheek Injections 10001

Subject Self-Assessment of Results

Patient Number				
Date:				
Baseline or Date post Or: Date Post 2 nd Injection	-	line 4 w 8 8w 12 w_		16 week
©Merz ©Merz	OMerz	SMerz	CMerz CMerz	CMerz CMerz
3	1	1	3	1
0	1	2	3	4
No sagging	Mild sagging	Moderate sagging	Severe sagging	Very severe sagging
Grading of Jowls Instructured above, put an				
1 2	34	_ 5		
Grading of Jowls by p yourself prior to inject putting an X by the va	ion and the photogra	ph of yourself today, p	olease evaluate your	
Much improved Improved No change Worse Much Worse	-			
Comments:				
Signature of Coordi	nator	Date:		

	Iowl/Jawline Study Iumber	10001-Patient Diary		Date
	e treatment			
many da	ys it has been since	= :	ne questions v	patient number, the date, and how which require to answer mild,
• N	Moderate: minimal,	and/or local or noninva out not immediately life	sive intervent	only; no intervention needed tion needed nospitalization or prolongation of
Have y	you experien	ced any of the fo	ollowing s	symptoms?
	oderate to Severe Di yes was it Mild	zziness Moderate		NO
	onfusion yes was it Mild	Moderate		NO
		s in your arms or legs Moderate		
	nanges to consciousn yes was it Mild	ess or alertness Moderate		NO
		eech impairment Moderate		
If		Moderate	Severe	
				bove questions, pleas
 1811 91 2 2 2 2 2 2 2 2 2 2 2 2 2 2 2 2 2 	L1 and seek i	mmediate medi	cal attent	ion.
sp	ots, problems movin		YES	ain in or around your eye, blindness, NO
		any portion of the face? Moderate		
• Cr	rusty or scabby skin a	round the eyelids or any o		e face NO
Ify	es was it Mild	Moderate		

		in in any area?	YES	_ NO	_
	If yes was it Mild	Moderate	Severe		
•	Moderate to Severe He			NO	_
	If yes was it Mild	Moderate	Severe		
•	Fever			_ NO	_
	If yes was it Mild	Moderate	Severe		
•	Difficulty Chewing or Sv	vallowing	YES	NO	_
	If yes was it Mild	Moderate	Severe	.	
•	Moderate to Severe Pa	in in Jaw at Rest	YES	NO	
	If yes was it Mild				
*If	you have answ	ered yes to ar	ny of the abo	ve ques	tions, please c
ie d	office immedia	tely at [name] durin	g busine	ess hours, or D
	at [name]				-
и и к	[name]	do il alter liot	 		
	These questions will any of the following	•	vents that may occ	ur. Please le	et us know if you have
1.	Have you noticed an				NI -
	•	y other symptoms no	ot listed above?		
	If yes, list symptoms				
	If yes, list symptoms If yes was it Mild Have you had any co	Moderate_	Severe since your last diar	y? Yes	 No
2.	If yes, list symptoms If yes was it Mild Have you had any co If yes, please list Have any symptoms	Moderate_ ontinuing symptoms s	Severe since your last diar	y? Yes	No
2.	If yes, list symptoms If yes was it Mild Have you had any co If yes, please list Have any symptoms If yes, please list Any change in medic	Moderate_ ontinuing symptoms s /side effects subside	Severe since your last diar	y? Yes Yes	No
2.	If yes, list symptoms If yes was it Mild Have you had any co If yes, please list Have any symptoms If yes, please list Any change in medic Yes No	Moderate_ ontinuing symptoms s /side effects subside	Severe since your last diar diary?	y? Yes Yes lications sin	No No No ce your last visit or di
2.	If yes, list symptoms If yes was it Mild Have you had any co If yes, please list Have any symptoms If yes, please list Any change in medic Yes No If yes, list medication Have you been diagnorms	Moderate_ontinuing symptoms solutions symptoms solutions subside cations, including over the cations of t	Severe since your last diary? d since last diary? er the counter medical conditions	y? Yes Yes lications sin	No No ce your last visit or di
 3. 4. 	If yes, list symptoms If yes was it Mild Have you had any co If yes, please list Have any symptoms If yes, please list Any change in medic Yes No If yes, list medication Have you been diagnorms	Moderate_ ontinuing symptoms s /side effects subside cations, including ove	Severe since your last diary? d since last diary? er the counter medical conditions	y? Yes Yes lications sin	No No ce your last visit or di
 3. 4. 	If yes, list symptoms If yes was it Mild Have you had any co If yes, please list Have any symptoms If yes, please list Any change in medic Yes No If yes, list medication Have you been diagr Yes No Have you had any ill	Moderate_ ontinuing symptoms s /side effects subside cations, including ove ns nosed with any new r If yes, please list	Severe since your last diary? d since last diary? er the counter medical conditions	Yes lications sin since your Yes	No ce your last visit or di

· - ·	Worst Pain 6 7 8 9 10 6 8 10			
9. Are you experiencing any of the	ne following today:	V.	NI.	
Bruising Mild	NA sala wata		No	-
■ Redness	Moderate	Severe_		
	Moderate	Severe		
■ Firmness				
If yes was it Mild	Moderate	Severe_		
Lumps/Bumps				
If yes was it Mild	Moderate	Severe_		
Itching				
If yes was it Mild	Moderate	Severe_		
Do you feel comfortable going out in				
f not, why not?				_
any other observations or comment y	ou have?			

Jowl Improvement with Injectable Fillers: Jawline Injections alone vs Jawline and Cheek Injections-Operative Note

Subje	ct#	Date_	Stop Time of Inje	action		
				oluma	-	
on the repres	diagran ented by ction as	n by the injector y the labels belo abbreviated her	indicating the below	labels (A1-D2) tten into the bo	. The amount (co	nted by hand drawing) placed in each area injector and the depth
A1:		_cc SC (circle one	both)			
A2:		_cc SC (circle one	both)			
B1:		cc SC (circle one	both)			
B2:		cc SC (circle one	both)		2 may	1 Comment
C1:	P -	cc SC (circle one	both)	V		
C2:	P -	cc SC (circle one	both)			
D1:	P -	cc SC (circle one	both)			
D2:	P -	_cc SC (circle one	both)			
Signat	ture	[name], N	Date _		_	

Cranial	Nerve	Eva	luations	CRF
---------	-------	-----	----------	------------

Subj	ect Number:	Date:	Visit Type:

Cranial Nerves II-VII; IX, X, XII Evaluation Criteria					
Cranial Nerve	Nerve Name	Function	Test		

ASSESSMENT OF CRANIAL NERVES II-VII; IX, X, XII

 	Optic Nerve Oculomotor Nerve	Pupillary reaction to light and accommodati on Extraocular	Tell the subject to look into the distance. Shine a bright light obliquely into each pupil. Look for: Direct light reflex – Pupillary constriction in the same eye. Consensual reaction – Pupillary constriction in the opposite eye. Accommodation – move the penlight toward the nose and observe pupillary constriction.
III IV VI	Oculomotor Nerve Trochlear Nerve Abducens Nerve	movements	Stand two feet directly in front of subject. Use your finger to make a horizontal sweep from the subject's left to the right at the level of the subject's eyes. Repeat this horizontal sweep at the level of the forehead and the chin. Look for normal conjugate movement of the eyes in each direction or any deviation from normal. A few beats of nystagmus on far lateral gaze is normal.
V	Trigeminal Nerve	Motor	Ask the subject to clench their teeth. Palpate the temporal and masseter muscles and note strength of muscle contraction.
		Gross sensation	Tell subject to close their eyes. Using a cotton swab stick or similar object, touch the subject's forehead, cheeks and jaw with the dull cotton end and the sharper wooden end in random fashion. Ask the subject to say if they feel the object is dull or sharp. Compare sensation on both sides of the face.
VII	Facial Nerve	Motor	The Regional House-Brackmann Facial Nerve Grading System will be used to evaluate the facial nerve branches at rest and during conversation with the subject. Ask the subject to: Raise both eyebrows Frown Close both eyes tightly while Investigator tries to open eye lids Show both upper and lower teeth Smile Puff out both cheeks
X X	Glossopharyngeal Nerve Vagus Nerve	Gagging, swallowing (gross sensation and motor); Speech	Ask subject to swallow while palpating front of the neck. Subject should have no issues or discomfort when swallowing. (Assess gag reflex if patient reports changes from baseline and if there is reason to suspect related pathology). Ask subject to say "Ahhh". The uvula should elevate symmetrically as a normal response. Subject should have no difficulty or impairments when speaking. Note if hoarseness is present.
XII	Hypoglossal	Tongue Movement (Motor)	Ask patient to stick their tongue out and have them move side to side, from cheek to cheek. Tongue movements should be symmetrical.

Rating/Description

1 = Normal

3 = Abnormal, clinically significant

2 = Abnormal, not clinically

significant

4 = Not assessed

Cranial			Result Score each side for each nerve function	
Nerve #	Nerve	Function Score each side for each nervice Right Side of Face Pupillary Reaction to Light and Accommodation Extraocular Movements Motor Gross Sensation Complete Regional House-Bracks		
Nerve #			Left Side of Face	
II	OPTIC	Pupillary Reaction to Light		
Ш	OCULOMOTOR	and Accommodation		
Ш	OCULOMOTOR			
IV	TROCHLEAR	Extraocular Movements		
VI	ABDUCENS			
V	TRIGEMINAL	Motor		
V	TRIGEMINAL	Gross Sensation		
VII	FACIAL	Motor	Complete Regional House-Brackmann Facial Nerve Grading System	
IX	GLOSSOPHARYNGEAL	Gross Sensation and Motor		
x	VAGUS	Gross Sensation and Motor		
XII	HYPOGLOSSAL	Motor		

Subject Number:	Date:	Visit Type:
Subject Number:	Date:	Visit Tyne:

REGIONAL HOUSE-BRACKMANN FACIAL NERVE GRADING SYSTEM

VII - Facial Nerve Assessment (Motor function)

	Score each side of face for each region		
Region and Score Description	Right Side of Face	Left Side of Face	
Forehead			
1 = Normal forehead movement			
2 = Slight weakness in forehead movement			
3 = Obvious but not disfiguring asymmetry with motion, symmetric at rest			
4 = Obvious weakness of disfiguring asymmetry with motion, symmetric at rest			
5 = Barely perceptible motion in forehead, asymmetric at rest			
6 = No movement			
F			
Eye			
1 = Normal eye closure			
2 = Mild weakness in eye closure			
3 = Obvious weakness but able to close eyes			
4 = Unable to close eye with maximal effort			
5 = Barely perceptible eyelid movement			
6 = No movement			
Midface			
1 = Normal midface movement			
2 = Slight weakness in midface movement			
3 = Obvious but not disfiguring weakness, symmetric at rest			
4 = Obvious weakness and disfiguring asymmetry with motion, symmetric at rest			
5 = Barely perceptible motion in midface, asymmetric at rest			
6 = No movement			
Mouth			
1 = Normal corner of mouth movement			
2 = Slight weakness of corner of mouth movement			
3 = Obvious but not disfiguring weakness, symmetric at rest			
4 = Obvious weakness and disfiguring asymmetry with motion, symmetric at rest			
5 = Barely perceptible corner of mouth movement, asymmetric at rest			
6 = No movement			
Synkinesis			
(voluntary muscle movement causing the simultaneous involuntary contraction of other muscles)			
1 = None			
2 = Mild - obvious but not disfiguring			
3 = Severe - disfiguring or interferes with function			

Saf	fety Eye Exams	
1.	Snellen Visual Exam:	
	RIGHT EYE : 20/10 20/15 20/20 20/40	TIME:
	LEFT EYE: 20/10 20/15 20/20 20/25 20/30 20/40	TIME:
2.	Ocular Motility Exam:	
	RIGHT EYE: Elevation Central: Normal Abnormal Elevation Upper Lateral Quadrant: Normal Abnormal Elevation Upper Medial Quadrant: Normal Abnormal	TIME:
	Depression Central: Normal Abnormal Depression Inferior Lateral: Normal Abnormal Depression Inferior Medial: Normal Abnormal Change from Previous Exam: Yes No	
	LEFT EYE: Elevation Central: Normal Abnormal Elevation Upper Lateral Quadrant: Normal Abnormal Depression Central: Normal Abnormal Depression Inferior Lateral: Normal Abnormal Depression Inferior Medial: Normal Abnormal Change from Previous Exam: Yes No	TIME:
•		
3.	RIGHT EYE: Right upper outer quadrant: Normal Abnormal A	TIME:
	LEFT EYE: Right upper outer quadrant: Normal Abnormal Ab	TIME:

Physica	al and Visual Exam		
	ual Evaluation:		
Is A	any Drooping of the Face Observed	Yes	No
	There Any Change in Skin Color Around the Eyelids	Yes	No
	here any Crusty or Scabby Skin Around the Eyelids	Yes	No
	y Other Observations or Notes	Ves	No
1 111,		100	
-			
-			
Wa	s Evaluation of Neurological Function Completed	Yes	No
Not	es:		
 			
			
TMIE	1		
TMJ E			
TMJ e	xamination begins with palpation of the muscles in the	face and neck regions.	
Palnati	ion of the Right masseter muscle:		
•	Pain: YesNoExplain_		
	111111111111111111111111111111111111111		
	ion of the Left masseter muscle:		
•	Pain: YesNo Explain		
•	Masses: Yes No		
	······································		
1	Patient open and close mouth:	Yes No	
	Normal range of motion:	Vos. No.	
		Yes No	
3.	Pain with opening or closing mouth:	Yes No_	
	Explain		
4.	Any reported problems with chewing or swallowing:	YesNo_	
	Any pain with chewing?	Yes No_	
			
	Explain		
			
		3 7	
Any ot	her observation?	Yes No	

PAIN ASSESSMENT FORM CRF

Subject	Date:				
1.	Are you experiencing any pain today? Yes No * If yes please answer the following questions.				
2.	Where is your paint located?				
3.	When did your pain begin?				
4.	Does the pain radiate or travel to other areas?				
5.	Is your pain: (please check answer) o Intermittent o Continuous o Both?				
6.	Does your pain vary in intensity? o Yes o No				
7.	Rate the intensity of your pain:				
No Pain	Moderate Worst Pain Pain				
0 1	2 3 4 5 6 7 8 9 10				
60					
(@	$(\mathscr{Q})(\mathscr{Q})(\mathscr{Q})(\mathscr{Q})(\mathscr{Q})$				
0	2 4 6 8 10				
8.	How does your pain affect your lifestyle? (↑, ↓ , no change)				
Choose	☐ Sleep?				
	Appetite?				
	Activity?				
